2.5 Randomization

Randomization will be performed by the randomizer of the Medical University of Vienna; subjects will be stratified by parity (Primipara / Multipara) and randomized in blocks of four. All subjects will receive a unique study number.

To prevent unmasking the actual procedures, the medical records will indicate the actual surgical procedure without stating the suture material used for anterior colporrhaphy. Intraoperative data collection will be conducted by the study surgeon rather than by other research staff.

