2.6 Intervention

Sacrospinous hysteropexy will be performed in a traditional and standardized manner in accordance with our surgical policy. Any other concomitant procedures (e.g.,

anterior and/or posterior colporrhaphy, cystoscopy, etc.) will be performed in accordance with each surgeon's preferred technique.

Operative management: All patients will be operated by the vaginal route. They are prepared under strict aseptic conditions in the dorsal lithotomy position. The bladder is emptied preoperatively with a thin disposable catheter and antibiotic prophylaxis (cefazolin) is administered before incision. A vasoconstricting solution (combination of vasopression and NaCl) is administered and a high posterior colpotomy is made towards the posterior cervix. Blunt preparation towards the right Spina ischiadica to visualize the right sacrospinous ligament. Once 4 cm of ligamentum sacrospinale are visualised, two sutures will be placed through the ligament approximately 2 cm medial of the spina ischiadica. Depending on preoperative randomization, patients will receive either PDS sutures (PDS 0) or prolene (2-0) sutures. This suture will then be placed through the posterior cervical wall, but not yet knotted. First, the colpotomy will be closed via absorbable sutures (2/0 vicryl). Should additional procedures such as anterior and/or posterior colporrhaphy be indicated, they will be performed at this stage. Only after, the pre-laid fixation sutures will be tied, whereby the portio will come to lie about 4-6 cm cranial of the level off the vulva towards the sacrospinous ligament. Participating surgeons will be defined as high volume surgeons in prolapse surgery and will also be part of the urogynaecologic core team.

Perioperative management: is also standardized and includes preoperative single-shot antibiotics as well as vaginal pack and an indwelling urinary catheter for 24 hours after the surgical procedure. Patients will have postvoid residual volume measurement at the first postoperative day (when urinary catheter is removed). A postvoid residual volume of $2 \times < 150$ ml is defined as normal and no further follow-ups are necessary. Postvoid residual volumes of > 150 mL or greater will be

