2.8 Data collection

At baseline, the following data will be collected: demographics and medical history data (age, body mass index, parity, menopausal and hormone therapy status, nutritional status, current smoking, previous hysterectomy and previous anti-incontinence surgery), and medical comorbidities (diabetes mellitus, connective tissue disorders), and data from the standardized urogynaecologic examination (POP-Q examination during maximal Valsalva, genital hiatus measurements and ultrasound of cervix, uterus, bladder, pelvic floor muscles and levator ani muscle hiatus).

Urogynaecologic examination evaluations is made using the POP-Q measurement system on maximum Valsalva effort in the seated semi-lithotomy position (a 45° upright sitting position). Objective anatomical cure is defined as a Ba point < -1. Symptoms, quality of life and sexuality are evaluated with the Deutscher

Beckenboden-Fragebogen. This Pelvic Floor Questionnaire consists of four domains: bladder, bowel, pelvic organ prolapse and sexual function. In every domain various questions assess severity and condition-specific quality of life. Every question is scored on a scale from zero to four. The sum of each individual domain is divided by the maximum reachable score and multiplied by ten, giving a value between zero (0=no symptoms) and ten (10=maximum of symptoms) for each of the domains. Baessler et al. has published the results of the validation study and scoring system [11].

To evaluate nutrition status, patients will receive the "Mini Nutritional Assessment"-Fragebogen (<https://www.dgem.de/sites/default/files/PDFs/Screening/MNA-SF%20Deutsch-240513.pdf>) and laboratory testing of albumin, electrolytes (sodium, potassium, magnesium, phosphate, and calcium), haematocrit, creatinine, blood urea nitrogen, and bilirubin.

Patients will be asked to complete the standardised Visual Analog Scale (VAS), Numeric Rating Scale (NRS) [13] and answer the following questions:

- "Do you experience a sensation of bulging or protrusion from the vagina?" and "Do you have a bulge or something fallen out that you can see in the vagina?" [6]
- "Do you experience pain in the rump?" and "Do you experience pain in the lower back?" and "Do you experience pain while walking?" [6]
- "What rate of postoperative recurrence would you accept and still opt for the surgery?" [14].

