2.8 Primary and secondary outcome measures

The primary outcome is subjective symptom improvement (evaluated by the prolapse domain score of the Deutsche Beckenboden Fragebogen) assessed at 12 months after surgery.

The secondary outcomes are the anatomical outcomes (the rate of suboptimal anatomical outcome in each compartment (POP-Q point, change in POP-Q values from baseline), condition-specific quality of life (any changes in questionnaire Deutscher Beckenboden Fragebogen from baseline), postoperative complications (haematoma, vesico-vaginal fistula, ureteral obstruction, urinary tract infection, incomplete bladder emptying, overactive bladder or stress incontinence symptoms, suture erosion, vaginal wound dehiscence, infection or granulation tissue, etc), and use of pain killers during the hospital stay. In addition, patients' pain level will be assessed through the standardised Visual Analog Scale (VAS), Numeric Rating Scale (NRS) [13] and the earlier specified questions, patients' improvement rate will be assessed through the "Patient Global Impression of Improvement (PGI-I).

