2.10 Data analysis

Statistical analysis will be performed using SPSS and Excel software. Data will be calculated and graphed as mean plus minus standard error of mean (SEM).

Metric variables will be reported by mean and standard deviation resp. median and IQR, categorical variables will be reported by frequencies per group and timepoint. The primary outcome subjective symptom improvement after 12 months in either group will be analyzed by a t-test or a Man-Whitney-U-test depending on the distribution of improvements.

For the secondary endpoints, differences of rates of adverse events between the two treatment groups will be analysed by a Chi-squared test. Blood loss, use of pain killers and changes in condition-specific quality of life will be compared between groups analogously to the primary outcome.

Changes in POP-Q values from baseline over time will be analysed by a linear mixed model with fixed effects group, time, POP-Q point, age and BMI and random effect intercept per patient. Statistical significance will be set 0.05. No correction for multiple testing is performed because only one main hypothesis is considered.

3. Research facility

The patient screening will be performed at the urogynaecologic outpatient clinic of the Department of General Gynaecology and Gynaecologic Oncology, Medical University of Vienna, Austria. Infrastructure needed for this study is already present.

4. Ethical and legal aspects

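### The secondary POP-Q change model leaves out the baseline value of the modelled point and the parity stratum, so it gives up precision that data already collected could supply

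*Combined protocol and SAP*

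**What the plan says.** Section 2.8 (Primary and secondary outcome measures) makes anatomy a secondary outcome: "the rate of suboptimal anatomical outcome in each compartment (POP-Q point, change in POP-Q values from baseline". Section 2.10 states the method, "Changes in POP-Q values from baseline over time will be analysed by a linear mixed model", and lists the terms in full: "fixed effects group, time, POP-Q point, age and BMI and random effect intercept per patient".

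POP-Q point in that list identifies which point was measured. It is not the baseline value of that point.

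Both missing variables are available. Section 2.8 (Data collection) records "POP-Q examination during maximal Valsalva, genital hiatus measurements" at baseline, and parity with the demographics. Section 2.5 uses parity in the allocation: "subjects will be stratified by parity (Primipara / Multipara) and randomized in blocks of four". No other section adds either variable to the model.

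**The concern.** A comparison of changes subtracts each woman's baseline in full, which is efficient only if the postoperative value follows baseline with a slope of 1. If the slope differs from 1, part of the baseline spread stays in the outcome as noise unrelated to the suture. A baseline difference that arises by chance between the arms then shifts the estimated group difference.

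The random intercept does not remove this. It accounts for correlation among one woman's measurements, but that patient-level variance remains in the comparison between arms.

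The plan already adjusts for age and BMI, so adjustment as such is accepted. The covariate most directly tied to the outcome and the only stratification factor are the ones left out. At stake is the precision of the trial's objective anatomical comparison, which has few patients.

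**Working it through.** **The plan's own figures.** No sample size or power is stated for POP-Q. For the questionnaire score, section 2.9 assumes SD 2.2 before and after and a correlation of 0.5. The SD of change is √(2 × 2.2² × (1 − 0.5)) = 2.2. For a difference of 2, two-sided 0.05 (sidedness is not stated) and 80% power, the t-test needs 20.002 per group, rounded up to 21, with power 0.820. The plan's 21 reproduces. The values r = 0.5 and 21 per group are borrowed below; neither is a POP-Q figure.

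**Formulas, one point at one visit.** Let r be the pre-post correlation and k the postoperative SD divided by the baseline SD. In units of the baseline variance:

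- variance of change: 1 + k² − 2rk
- residual variance after baseline adjustment: k²(1 − r²)
- ratio, adjusted to unadjusted: k²(1 − r²)/(1 + k² − 2rk)
- pre-post slope: rk; share of a baseline difference carried into the change difference: 1 − rk, with reversed sign

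Age, BMI and the degrees of freedom spent are ignored.

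**Worked case, k = 1, r = 0.5.** The ratio is 0.75/1.0 = 0.75. The standard error ratio is √0.75 = 0.866, a reduction of 13.4%. With 21 per group the standard error falls from √(1.0 × 2/21) = 0.309 to √(0.75 × 2/21) = 0.267 SD. The difference detectable with 80% power (2.802 times the standard error, normal approximation) falls from 0.87 to 0.75 SD.

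**Reduction in standard error over assumed values**

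| k | r = 0 | r = 0.2 | r = 0.5 | r = 0.7 |
|---|---|---|---|---|
| 0.8 | 38% | 32% | 24% | 21% |
| 1.0 | 29% | 23% | 13% | 8% |
| 1.25 | 21.9% | 14.7% | 5.5% | 1.0% |
| 1.5 | 16.8% | 9.7% | 1.8% | 0.1% |

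The ends of the range are k = 0.8, r = 0: √(0.64/1.64) = 0.625; and k = 1.5, r = 0.7: √(1.1475/1.15) = 0.999.

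**Carry-over, 1 − rk.** With k = 1 it is 50% at r = 0.5 and 30% at r = 0.7. With k = 0.8 it is 84% at r = 0.2 and 44% at r = 0.7. With 21 per group, a chance baseline difference has SD √(2/21) = 0.31 baseline SD and exceeds 0.5 SD in either direction in about 10.5% of randomisations. At k = 1 and r = 0.5, a difference of 0.5 SD moves the change difference by 0.5 × 0.5 = 0.25 SD.

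**Pooled coefficient.** The planned model has one group effect over all points and visits, which the figures above do not describe. A simulation of that coefficient used 3 points, 3 visits, 21 per group, equal SDs, and assumed correlations of 0.4 between points and 0.7 between follow-up visits. It gave variance ratios, adjusted to unadjusted, of 0.55, 0.70 and 0.82 at r = 0.2, 0.5 and 0.7. The loss therefore persists under those assumptions with repeated measurements.

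**Parity.** If the two strata differ by d residual SDs and a proportion p is primiparous, adjustment removes d²p(1 − p)/(1 + d²p(1 − p)) of the variance. With d = 0.5 assumed, this is 0.04/1.04 = 3.8% at p = 0.2 and 0.0625/1.0625 = 5.9% at p = 0.5. It is 0% if parity is not prognostic.

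**The case against.** The strongest reply is that the gain may be small. The inclusion criteria in section 2.7 require Aa or Ba above 0 and C above 0, which can narrow the baseline spread of these points, while postoperative values carry no such limit. Postoperative SD may then exceed baseline SD, and at k = 1.25 the reduction is only 14.7%, 5.5% and 1.0% at r = 0.2, 0.5 and 0.7. This stands, and the table includes those rows for that reason.

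A reader might infer a low correlation from section 2.6, where "the portio will come to lie about 4-6 cm cranial of the level off the vulva". The documents do not support that step. The target spans 2 cm, concerns the cervix when the sutures are tied, and says nothing about 6 or 12 months or about the vaginal wall points, which the model pools with C.

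A reader might also infer that the planned analysis is much less precise than it could be, or that most of any baseline imbalance passes through. Both hold only when the correlation is low.

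On parity, stratified blocks of four already limit imbalance, and the documents give no sign of how prognostic parity is. This also stands, and makes parity the lesser part.

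Finally, the outcome could be read as raw POP-Q values with baseline as one level of time. Baseline would then be an outcome row and could not simply be added as a covariate, so the fix has to define the outcome.

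**Conclusion.** Both omissions are in the text, and adding the terms is a nearly free improvement in precision for a secondary outcome. At equal SDs and r = 0.5 the standard error for one point at one visit falls by about 13% and carry-over without adjustment is 50%. The plausible range of the reduction runs from about 0% to 38%. These sizes rest on assumed SDs and correlations, because the documents give none for POP-Q.

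It would go too far to call the planned analysis biased or invalid. Randomisation keeps the group estimate unbiased on average, and the imbalance effect is conditional on the baseline difference that happens to occur. Nor does the point reach the primary questionnaire comparison, which has its own test, or the 21 and 26 per group in section 2.9.

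**What to change.** In section 2.10, state that the POP-Q outcome is the change from baseline at each post-baseline visit (4-6 weeks, 6 months and 12 months), so that baseline is not also an outcome row. List the fixed effects as group, time, POP-Q point, baseline value of the same POP-Q point with its own slope per point, parity stratum, age and BMI, with the random intercept per patient. Fixing this in advance also avoids a later choice between adjusted and unadjusted results.

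The change takes a sentence or two, needs no new data and alters no procedure. The cost is one slope per POP-Q point and one parity term, a few degrees of freedom. The gain from the baseline term disappears only as the pre-post slope approaches 1; the parity term helps only if parity is prognostic.

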4.1. Risks

The expected risk for the subjects involved in the study can be considered as minimal. Sacrospinous hysteropexy will be performed as a standard procedure. This procedure is clinical standard of care and is not an additional study related procedure. It is unclear if different suture material led to different adverse effects.

The only possible risk that patient's data might be released to public is minimized by anonymization of all data that will be saved at a password secured server. Data will be accessible by authorized staff only.

4.2. Publication of data

The results of the study will be published in an adequate timeframe.

4.3. Changes of the study protocol

If changes of the study protocol should occur, they will be documented carefully. If significant changes should be necessary, the ethic commission will be contacted and asked for permission.

4.4. Protection of data privacy

All data obtained from the subjects in this study will be handled with care and will not be passed to a third person. Every individual will be given a unique code to ensure the protection of personal data sample evaluation.

